Statistical approach. To study the gene expression profiles that are related to the 3-month rosiglitazone intervention, we will compare the expression profile of the muscle (and fat) tissues from pretreatment subjects to that from post-treatment subjects. We will calculate and normalize gene expression levels by the Robust Multichip Average method (RMA) (37) and quantile normalization (11). The statistical significance of these comparisons will be assessed using LIMMA package software (27) (a linear model approach implemented in Bioconductor) or non-parametric methods (e.g., Kruskal-Wallis- or Mann-Whitney U-tests), using SAS software. A critical issue in microarray analysis is to avoid a high "false discovery rate" (9) (FDR; the probability that a gene is incorrectly identified as differentially expressed), due to the large number of genes compared. We will consider genes to be differentially expressed only if they meet criterion values for fold-change and p-value (for example, >1.5 and <0.05, respectively). For each analysis of differential expression, we will experiment with different combinations of criterion values and calculate the resultant FDR (using MULTTEST package in Bioconductor (61)) for each set of criteria, until we obtain acceptable stringency for fold-change, statistical significance and FDR (we anticipate using conservative FDRs in the range of 1-5%).

To study the association between these differentially expressed (DE) genes and the response of the primary and secondary traits to TZDs, for each DE gene, we will generate linear regression models using the change in the response of the primary (i.e., insulin sensitivity) and secondary responses to TZDs as dependent variables and the gene expression change in response of the treatment and demographic and clinical measures as the independent variables. For the regression models, we will report the adjusted squared correlation coefficient (R^2_{adj}), which corrects for the degrees of freedom. The association between each DE gene and each trait in response to TZDs can be measured by the adjusted squared correlation coefficient. The overall association with primary and secondary traits can be based on the score that is calculated as the weighted sum of the corresponding the adjusted squared correlation coefficients. The weights can be determined by principal component analysis. The importance of each gene can be determined by its score.

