We will validate the SNPs identified by sequencing and/or in silico SNP discovery by genotyping a subsample of 96 individuals (48 European Caucasians and 48 African Americans) selected also from our DNA repository. We anticipate that on average, we will have identified 20 SNPs per gene, requiring us to genotype \approx 2,000 SNPs/person (100 genes \times 20 SNPs/gene). Allele frequencies of SNPs and linkage disequilibrium (LD) between intragenic SNPs will be calculated. This information will be used to choose haplotype-tagging SNPs for genotype analysis in the larger sample. With allele frequency and linkage disequilibrium information, we will be able to eliminate some SNPs from subsequent analysis. For example, SNPs with allele frequencies < 5% or SNPs in high LD (e.g., $r^2 > 0.7$) with other SNPs will not be genotyped in the larger cohort. We will use algorithms to select haplotype-tagging SNPs to maximize the likelihood that we have captured most or all of the sequence variation. Haplotype-tagging SNPs (ht-SNPs) will be genotyped in three different population groups as described in the following section. The Illumina platform will be used for this large-scale genotyping effort, which will be performed at the Broad Institute of Harvard and MIT (see Letter from [name]).

4. Specific Aim 3. Association Analysis of Candidate Genes with TZD Response in Three Populations

We will genotype the htSNPs identified in Specific Aim 2 in three separate populations who have undergone a TZD intervention. Approximately 1,500 htSNPs from 100 genes will be genotyped in: (1) 75 subjects recruited for this study; (2) 597 troglitazone-treated individuals from the Diabetes Prevention Program, or DPP; and (3) 97 gestational diabetic Hispanic women who were treated with troglitazone (and more recently pioglitazone) from the TRIPOD/PIPOD study.

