Subjects were eligible for DPP if their age was \geq 25 years, BMI was \geq 24 (\geq 22 for Asian-Americans), and they had impaired glucose tolerance plus a fasting plasma glucose of 95-124 mg/dl (or \leq 124 mg/dl for American Indians). Among randomized subjects, 55% were Caucasian, 20% were African-American, 16% were Hispanic, 5% were American Indian, and 4% were Asian-American. Their average age at entry was 51 ± 10.7 years (mean \pm SD), and 67.7% were women. Of the women, 48% were postmenopausal. Overall, BMI averaged 34.0 ± 6.7 at baseline with 57% of the men and 73% of women having a BMI \geq 30. Average fasting plasma glucose (108 ± 9 mg/dl) and HbA1c ($5.9 \pm 0.5\%$) in men were comparable with values in women (106 ± 7 mg/dl and $5.9 \pm 0.5\%$, respectively). For TRIPOD, Hispanic women (of Mexican and Central American origin) in the Los Angeles area were eligible if they were \geq 18 years of age, had GDM in the previous 4 years, and were willing to use effective contraception. They were offered participation in the study if they had no evidence of chronic disease; a serum alanine aminotransferase concentration < 1.5 times the laboratory upper normal; no diabetes; and a sum of five oral glucose tolerance test (OGTT) plasma glucose concentrations \geq 625 mg/dl, predicting a 70% risk of diabetes in the next 5 years. Enrollment continued until 266 women had

been randomized. Mean age was 34.9 ± 6.6 yrs, BMI 30.6 ± 6.1 , fasting glucose 98.7 ± 10.2 mg/dl, 2-h glucose 154.4 ± 27.0 mg/dl. We have successfully extracted DNA on 217 women who completed the 3-month IVGTT assessment. After termination of the study, women who had not developed diabetes were invited to participate in an extension involving pioglitazone, PIPOD.

[name] (co-investigator) and [name] (consultant) are co-PIs on an NIH-funded grant to relate candidate genes to DPP data (see letter from [name]), while [name] (co-investigator) is PI of the data management and analysis subcontract for the study. The DPP genetics study includes the typing of population markers, which will be used in the proposed replication study. [name] has previously preformed a pharmacogenetic study involving the TRIPOD subjects.

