In each population separately, we will compare mean insulin sensitivity according to genotype using analysis of variance. We will include age and sex in the analysis as covariates. In additional models, we will add multiple genotypes from the same or related pathways and test their potential interaction effects in a multiplicative fashion. Prior to analysis, we will perform a series of routine quality control checks on the genotype data that will include a repeatability analysis of a panel of 5% duplicate samples, and chi-square tests to assess compliance of the genotype distributions with Hardy-Weinberg Equilibrium. These procedures are routinely carried out in our laboratory. The primary analysis will be to determine if there is a dose response effect of genotype on the outcome. This analysis is conducted by assigning codes of 0, 1, or 2 to the genotype, with the value of the code reflecting the number of (minor) alleles. In addition, we will also carry out secondary analyses of the dominant and recessive genetic models to evaluate the effects of the respective homozygotes on TZD response.

a. *Haplotype-disease association analysis*

Haplotypes may potentially provide more information about an unobserved causal variant than single SNPs because of the increased resolution of multiple SNPs considered jointly to tease out the unobserved ancestral haplotype background on which mutation arose and which is shared among affected individuals. We plan to use Helix Tree, a commercially available software package designed for managing and analyzing data from large-scale genome-wide association studies, for our haplotype analysis.

The haplotype trend regression analysis in Helix Tree regresses the response variable using the estimated haplotype probabilities as the regression matrix, thereby properly incorporating the uncertainty in individual haplotype assignment inherent in population-based data. We will compute permutation-derived empirical significance levels for each candidate gene to eliminate bias due to incorrect distributional assumptions.

b. *Population stratification*

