One potential pitfall of association studies in population-based samples is false-positive signals resulting from population stratification. We will use an Illumina panel of 278 ancestry informative markers from the HumanHap 550K chip (Illumina; San Diego, CA) to account for potential effects of population stratification in our analyses either by adjusting the variance of the statistic or by adjusting the populations (88, 89). We attempt to eliminate false positives by assigning higher priority to signals that are replicated in multiple populations either at the same SNP, same haplotype block or same gene. We recognize that these methods represent global adjustments based on genome-wide averages of admixture, thus do not provide information about the chromosomal region containing SNPs of interest. However, newer methods are beginning to appear that attempt to define the ancestral blocks to potentially allow for local admixture adjustment in case-control analyses (90). We plan to evaluate new methods as they become available and integrate those that will add power to our analyses.

c. *Power calculation for the candidate gene analyses*

We estimated the effect sizes we could reasonably expect to detect at 80% power in these three samples. The calculations were made across a range of allele frequencies, and for sample sizes of 75, 97, and 585, in the current study, TRIPOD, and the Diabetes Prevention Program (DPP), respectively. For purposes of these calculations, we further assumed a dominant genetic model in which mean TZD response levels were to be compared between two genotype groups (e.g., AA vs. Aa/aa). The effect sizes are parameterized to reflect the difference between the group means, expressed in terms of the

standard deviation units. By convention, differences between groups of 0.8 SD, 0.5 SD and 0.2 SD are considered large, medium, and small effects, respectively.

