For the current study ($n = 75$ subjects) and TRIPOD studies ($n = 97$ subjects), we would have 80% or higher power to detect medium size effects (0.7 SD unit differences between means) across a wide range of allele frequencies (i.e., minor allele frequencies 0.1-0.5). For a putative subgroup of the current study with $n=38$, we would have 80% or higher power to detect large effect sizes (1.0-1.2) across the same allele frequencies. For the DPP ($n = 597$ subjects), we would have 80% or higher power to detect small size effects (0.3 SD unit differences between means) also across a wide range of allele frequencies. It is also worth noting that subjects to be recruited from this study will have mRNA levels measured, a very proximal phenotype that can be used as an additional outcome for the genetic association studies. One might expect a very large effect of an associated SNP on this particular phenotype.

E. HUMAN SUBJECTS RESEARCH

Protection of Human Subjects

1. Risks to the Subjects

a. Human subjects involvement and characteristics

Inclusion criteria

- Male or female who self-identifies as (in NIH classification terms) White.
- Age 35 - 65 years
- BMI 25 - 40 kg/m²

The age and BMI criteria were chosen to favor subjects with a relatively high likelihood of having insulin resistance and chronic inflammation, which makes intervention clinically meaningful.

Exclusion criteria

- History of diabetes (Doctor told pt. they had diabetes or pt. is taking diabetes medication)
- Fasting glucose value diagnostic for diabetes
- 2-h oral glucose tolerance test diagnostic for diabetes
- Medications that the investigator judges will make interpretation of the results difficult or increase the risk of participation (e.g., anticoagulants)
- Disease that the investigator judges will make interpretation of the results difficult or increase the risk of participation (e.g., anemia, cardiac decompensation, intolerance to rosiglitazone, lidocaine or other agents used)
- Pregnancy
- Physical dimensions exceeding the limits of any equipment used

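### The Aim 3 replication screen accepts a match anywhere in the same gene, with no signal level and no allowance for about 15 htSNPs per gene

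*Combined protocol and SAP*

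**What the plan says.** Section D.4.b (Population stratification) of the combined protocol and SAP plans to adjust for ancestry with 278 markers. It then says false positives will be reduced by "assigning higher priority to signals that are replicated in multiple populations either at the same SNP, same haplotype block or same gene". No p-value for a signal is given, and the three kinds of match are not ranked.

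The size of the search is in D.4 (Specific Aim 3): "Approximately 1,500 htSNPs from 100 genes will be genotyped in" three cohorts, namely the 75 study subjects, DPP and TRIPOD. D.3.b (Specific Aim 2b) limits LD among those SNPs, because SNPs in high LD (r² above 0.7 is the example) "with other SNPs will not be genotyped in the larger cohort". D.4 makes the additive 0/1/2 test of each SNP the primary analysis, run in each population separately, and gives no significance level.

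Two other error controls appear:

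- D.4.a (haplotype analysis): "We will compute permutation-derived empirical significance levels for each candidate gene". The stated purpose is to avoid bias from wrong distributional assumptions. No cut-off is given, and there is no link to the single-SNP tests or to D.4.b.
- D.2.f (Statistical approach): "we anticipate using conservative FDRs in the range of 1-5" percent. This concerns differential gene expression.

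D.1 hopes for consistent evidence, for example altered mRNA together with association in both populations, without a threshold.

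**The concern.** A match at the same SNP gives chance one opportunity per SNP. A match anywhere in the gene lets any of about 15 SNPs signal in one cohort and any of the 15 signal in the other. At a nominal level the second is much weaker evidence, yet the rule gives both the same standing. Since no signal level is stated, a reader cannot tell how many replicated genes to expect when no gene has an effect.

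At stake is which of the 100 candidate genes look replicated at the end of Aim 3. D.4.b is the only replication screen stated for the single-SNP results.

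There is a related gap. D.2.e (Specific Aim 1c) chooses the genes by correlating expression change with clinical response in the 75 study subjects, and D.4 then uses the same 75 as an association population. The plan does not say that they are left out when replications are counted. Selecting genes in those people can inflate SNP-response hits for variants that affect expression change.

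**Working it through.** **Step 1. Which signal level fits the plan's own power figures?** D.4.c gives no alpha. It assumes a dominant model with minor allele frequency (MAF) q from 0.1 to 0.5. For DPP (n = 597) it says "we would have 80% or higher power to detect small size effects (0.3 SD unit differences between means"), and for n = 75 and n = 97 it claims at least 80% power for 0.7 SD.

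Group sizes are n₁ = n(1−q)² and n₂ = n − n₁, and the noncentrality is d·√(n₁n₂/n). For DPP at q = 0.1, n₁ = 483.6 and n₂ = 113.4, so the noncentrality is 0.3 × √91.9 = 2.88. Power at two-sided 0.05 is then about Φ(2.88 − 1.96) = 82%. Across q = 0.1 to 0.5, by noncentral t:

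| Cohort, effect | α = 0.05 | α = 0.01 |
|---|---|---|
| DPP, n = 597, 0.3 SD | 82–96% | 62–86% |
| TRIPOD, n = 97, 0.7 SD | 76–93% | 53–79% |
| This study, n = 75, 0.7 SD | 65–85% | 40–65% |

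The DPP statement reproduces at 0.05 and fails at 0.01 for some allele frequencies (62% at q = 0.1, 72% at q = 0.5). At 0.05/1,500 it would be about 10–30%. The n = 75 and n = 97 statements do not hold over the whole range even at 0.05. So 0.05 is the better fit, but it remains an assumption.

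**Step 2. Chance same-gene matches in DPP and TRIPOD.**

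- Inputs: 1,500/100 = 15 htSNPs per gene; one additive test per SNP; separate people in each cohort, so null results are independent between cohorts.
- With no LD, the chance that a null gene has at least one signal in one cohort is p = 1 − (1−α)¹⁵. At 0.05, p = 1 − 0.4633 = 0.537, and the expected matches are 100 × 0.537² = 28.8 genes. At 0.01, p = 0.140, giving 1.96 genes.
- With LD, p comes from simulating 15 correlated z-scores. The documents give no LD values beyond the example pruning limit, so the patterns below are assumptions.

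| LD within a gene | p at 0.05 | Matches per 100 genes at 0.05 | Matches at 0.01 |
|---|---|---|---|
| None | 0.54 | 28.8 | 2.0 |
| Decaying, adjacent r² 0.3 | 0.47 | 21.9 | 1.5 |
| Decaying, adjacent r² 0.5 | 0.40 | 16.3 | 1.1 |
| Decaying, adjacent r² 0.7 | 0.31 | 9.9 | 0.7 |
| Five blocks, r² 0.5 / 0.7 within block | 0.44 / 0.39 | 19.1 / 14.9 | 1.3 / 1.0 |
| Three blocks, r² 0.5 / 0.7 within block | 0.38 / 0.32 | 14.4 / 10.0 | 1.0 / 0.7 |
| All pairs r² 0.3 | 0.34 | 11.3 | 0.8 |
| All pairs r² 0.5 | 0.25 | 6.4 | 0.5 |
| All pairs r² 0.7 | 0.18 | 3.3 | 0.2 |

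Matches use unrounded p. D.1 gives 1,536 SNPs, or 15.4 per gene, which moves the no-LD figure only to 29.7.

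**Step 3. Same-SNP matches for comparison, at 0.05.** 1,500 × 0.05² = 3.75 SNPs, or 1,500 × 0.05 × 0.025 = 1.9 if the direction must also agree. They fall in 1.7 genes (all pairs r² 0.7) to 3.7 genes (no LD). Same-gene matching therefore gives from 3.3/1.7 = 1.9 to 28.8/3.7 = 7.8 times as many chance genes.

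**Step 4. A gene-wise p-value instead.** If p<0.05 already allows for all SNPs in the gene, matches in both cohorts are 100 × 0.05² = 0.25 genes. Adding same-SNP, same-direction matches at 0.05 as a second route gives 1.0 to 2.1 genes by either route.

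**Step 5. If the 75 subjects also counted.** A match in any two of three cohorts has probability 3p² − 2p³. With no LD, treating the 75 as a third independent null cohort, that is 0.864 − 0.309 = 0.555, or about 55 genes instead of 29.

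**The case against.** The strongest reply is that this is a way of ranking leads. It sits under population stratification, where agreement between cohorts of different ancestry does help, and it speaks of priority. That stands, and it keeps the point minor. A reader might infer that the plan would announce 10 to 22 false associations. The documents do not support that: no association is declared from a match, and 0.05 is nowhere stated. At 0.01 the count is at most 2.

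Second, D.4.a already plans a per-gene permutation level. If it defined a same-gene signal at 0.05, chance matches would be about 0.25. So it would be wrong to say the plan lacks a gene-level tool. The tool is simply not connected to the single-SNP tests or to the replication rule.

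Third, same-gene matching has a sound purpose. SNP validation and LD estimation use "genotyping a subsample of 96 individuals (48 European Caucasians and 48 African Americans"), while "For TRIPOD, Hispanic women (of Mexican and Central American origin) in the Los Angeles area were eligible". Different SNPs may tag the same causal variant in DPP and TRIPOD. This argues against dropping the same-gene tier or demanding a lead-SNP match only. Nor is the absence of a direction condition a fault of that tier: when different SNPs signal in the two cohorts there is no common direction to require. Direction matters only for same-SNP matches.

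Fourth, D.1 asks for mRNA evidence too, which would lower the chance counts. It is offered as an example within a hope and sets no threshold. Its reference to both populations, after naming DPP and TRIPOD, suggests that the 75 subjects were not meant to count, but the plan does not say so.

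**Conclusion.** The point holds as a minor one. The screen places same-SNP, same-block and same-gene matches side by side, without a signal level and without allowing for about 15 htSNPs per gene, and no other passage governs it. At an assumed two-sided 0.05 per SNP, with the additive test only and with DPP and TRIPOD only, about 10 to 22 of 100 null genes match by chance under decaying or block LD. The figure is 3 to 11 if all SNP pairs share r² of 0.7 to 0.3, and 29 with no LD. At 0.01, over the same LD cases, the figures are about 0.7 to 1.5, 0.2 to 0.8, and 2.0.

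The missing signal level and the unranked tiers are plain from the text. The counts are conditional on the assumed level and LD. The 0.05 level fits the DPP power statement but not the n = 75 and n = 97 statements at every allele frequency.

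**What to change.** 1. Extend the per-gene permutation of D.4.a to the maximum additive single-SNP statistic over each gene's htSNPs, adjusted for age, sex and ancestry.
2. Rank matches between DPP and TRIPOD in tiers. The top tier is either (a) the same SNP at 0.05 in each cohort, with the same allele and direction, or (b) the same gene or block with gene-wise permutation p<0.05 in both cohorts. Expected null genes per 100 are about 0.25 by (b) and 1 to 2 by either route. Other nominal same-gene overlaps stay listed as a lower, supportive tier, so they are not lost when tag SNPs differ by ancestry.
3. State that the 75 subjects used to select the genes do not count as a replicating population.

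The cost is analysis-plan wording and more permutation runs, with no new data or genotyping. The real downside is that fewer small-effect genes reach the top tier. In simulations with a 0.3 SD effect in both cohorts, 16–42% reach it, against 31–61% that show a nominal same-gene overlap (some of these through chance hits at other SNPs). If a different SNP tags the causal variant in each cohort, the figures are 5–30% against 23–55%. For 0.7 SD with the causal SNP typed they are 70–94% against 81–94%. This loss is the reason to keep the lower tier and not to replace the rule with a strict gate.

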correlated to TZD response will be defined as candidate genes and will be pursued using state-of-the-art molecular genetic approaches to define all common sequence variation and haplotype structure of the gene. We will then genotype these SNPs in our subjects to determine if these SNPs or haplotypes associate with TZD response. Although the 75 subjects we plan to recruit for this study will provide very rich phenotype and microarray information for defining TZD response and for selecting candidate genes to study, they will not be particularly powerful to discern the effect of specific gene variants on clinical response to TZDs.

However, they may be useful in discerning associations of gene variants with mRNA levels encoded by that gene (or within the same regulatory pathway). Thus, in the next stage of our study, we will take advantage of established collaborations with investigators of large prospective studies which involved a TZD intervention and for which relevant response traits have been collected, the DPP Study, and the TRIPOD Study (now continued as PIPOD).

[figure not shown]

Fig. 9. Timeline of the study

High throughput genotyping of 1536 SNPs in 100 candidate genes will be performed in these cohorts and association of SNPs and haplotypes with TZD response will be examined. It is our hope that in a subset of these 100 candidate genes we will find consistent evidence for a role in TZD response, e.g., altered mRNA levels in those with the variant SNP/haplotype and association with TZD response in both populations.

2. **Specific Aim 1. Defining interindividual variability in TZD response**

a. *Subject recruitment and screening*

Seventy-five subjects will be recruited for this study from the following sources:

- A large database belonging to the Division comprising over 500 subjects recruited at health fairs. These subjects have provided basic health information, given blood for genotyping, and indicated that we may contact them to inform them about future genetic studies. Additionally, some subjects have had oral glucose tests. We have previously successfully recruited subjects from this collection. This collection will also allow rapid identification of potential volunteers for our study if the focus should later change to a particular genotype or clinical profile.

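### At n = 75, the claim of at least 80% power for a 0.7 SD difference fails at both ends of the stated allele-frequency range

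*Combined protocol and SAP*

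**What the plan says.** Section D.4.c sets up the calculation as follows: "We estimated the effect sizes we could reasonably expect to detect at 80% power in these three samples". The sample sizes are given as "for sample sizes of 75, 97, and 585, in the current study, TRIPOD, and the Diabetes Prevention Program (DPP), respectively". The model is also given: "we further assumed a dominant genetic model in which mean TZD response levels were to be compared between two genotype groups", with the difference in means expressed in SD units. The benchmarks are that "differences between groups of 0.8 SD, 0.5 SD and 0.2 SD are considered large, medium, and small effects, respectively". No significance level or sidedness is stated for this calculation.

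The result for n = 75 and n = 97 together is "we would have 80% or higher power to detect medium size effects (0.7 SD unit differences between means) across a wide range of allele frequencies", and the range is spelled out as minor allele frequencies 0.1 to 0.5. For a possible subgroup of 38 subjects the plan says "we would have 80% or higher power to detect large effect sizes (1.0-1.2) across the same allele frequencies". For the DPP it claims 80% or more for 0.3 SD.

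Elsewhere, the study overview (D.1) says of the 75 subjects that "they will not be particularly powerful to discern the effect of specific gene variants on clinical response to TZDs". Specific Aim 3 (D.4) nevertheless lists them as one of three association populations.

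**The concern.** One effect size is quoted for two samples of different size, and a few sentences later the plan needs 1.0 to 1.2 SD for a sample about half as large as 75. Those figures do not sit together. Under a dominant model the two genotype groups are very unequal at MAF 0.1 and fairly unequal at MAF 0.5, so the ends of the range are where a claim for the whole range would be expected to break.

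What is at stake is how a non-significant SNP result in the 75 subjects is read. If power is 65% and not at least 80%, the chance of missing a true 0.7 SD effect is about 35%, where the plan implies at most 20%. Section D.4.b gives priority to signals that replicate across populations, so missed effects in this sample can affect which genes are taken forward. A reader who takes medium to mean 0.5 SD, as the section defines it, is further from the truth still.

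**Working it through.** **Inputs from the plan.** n = 75, 97, 38, and 585 or 597 (D.4.c uses both for the DPP); differences of 0.7, 1.0 to 1.2, and 0.3 SD; MAF 0.1 to 0.5; dominant two-group comparison; 80% power.

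**Assumptions.** Alpha is taken as two-sided 0.05 for one test, with one-sided 0.05 shown as the alternative. Carrier shares follow Hardy-Weinberg.

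**Formulae.** Carrier share f = 1 − (1 − MAF)². Group sizes are n·f and n·(1 − f). Power comes from a two-sample t-test with n − 2 degrees of freedom and noncentrality d·√(n·f·(1 − f)).

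**Does two-sided 0.05 reproduce the plan's other figures?**

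- n = 38, MAF 0.1: detectable difference 1.19 SD, against a stated upper end of 1.2. One-sided gives 1.05.
- DPP, 0.3 SD, MAF 0.1: power 81% (n = 585) or 82% (n = 597), against a stated 80% or more.
- Correlation of 0.31 at n = 75 (Analysis plan, D.2.e, Aim 1b): 79.6% two-sided against a stated 80%. One-sided gives 87.5%.

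The n = 38 upper end and the correlation figure point to two-sided 0.05. The DPP figure is consistent with it but does not settle sidedness.

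**The n = 75 claim, 0.7 SD, two-sided 0.05.** At MAF 0.1, f = 0.19, so the groups are about 14 and 61, and the noncentrality is 0.7 × √(75 × 0.19 × 0.81) = 0.7 × 3.397 = 2.38. At MAF 0.5, f = 0.75, so the groups are about 56 and 19, and the noncentrality is 0.7 × √(75 × 0.75 × 0.25) = 0.7 × 3.75 = 2.63.

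| MAF | f | Power, two-sided | Power, one-sided |
|---|---|---|---|
| 0.1 | 0.19 | 65% | 76% |
| 0.15 | 0.28 | 76% | 85% |
| 0.2 | 0.36 | 82% | 89% |
| 0.3 | 0.51 | 85% | 91% |
| 0.4 | 0.64 | 82% | 89% |
| 0.5 | 0.75 | 74% | 83% |

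Two-sided power equals 80% at MAF 0.178 and again at MAF 0.430. For 0.7 SD to reach 80% at MAF 0.1, two-sided alpha would have to be about 0.13. Letting the carrier count vary at random gives slightly lower values (64% at MAF 0.1 and 73% at MAF 0.5, by simulation).

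**Other readings at MAF 0.1, n = 75.** Normal approximation: 66%. Difference in total-SD units: 69%. Additive coding with 0.7 SD per allele: 73%. None reaches 80%.

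**Difference detectable with 80% power over MAF 0.1 to 0.5, two-sided.**

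| Sample | Smallest (MAF about 0.3) | Largest (MAF 0.1) | Plan states |
|---|---|---|---|
| n = 38 | 0.93 | 1.19 | 1.0–1.2 |
| n = 75 | 0.66 | 0.84 | 0.7 |
| n = 97 | 0.57 | 0.73 | 0.7 |
| DPP | 0.23 | 0.30 | 0.3 |

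**Check that needs no particular alpha.** If all samples were computed at the same level, detectable differences scale approximately with 1/√n. From the plan's n = 38 range: 1.0 × √(38/75) = 0.71 and 1.2 × √(38/75) = 0.85 SD at n = 75.

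**Effect of 0.5 SD (medium by the plan's benchmark), two-sided.** Power is 39 to 57% at n = 75 and 48 to 68% at n = 97.

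**The case against.** The strongest reply is that alpha and sidedness are not stated, so 65% and 74% are conditional. That stands, and it matters at MAF 0.5, where a one-sided test gives 83%. It does not rescue MAF 0.1, which fails one-sided at 76%. A related argument is rounding: one-sided, the largest detectable difference at n = 75 is 0.74 SD, which rounds to 0.7. But one-sided testing does not fit the plan's 1.2 SD for n = 38 or its correlation of 0.31, and the two-sided 0.84 SD does not round to 0.7.

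The fit to two-sided 0.05 is not perfect either: the smallest detectable difference at n = 38 is 0.93 SD, against a stated lower end of 1.0. The lower end of the rescaled range, 0.71 SD, agrees with 0.7, and rescaling a one-decimal figure is imprecise: 1.15 to 1.25 SD would give 0.82 to 0.89 SD. The disagreement is therefore at the unfavourable end, which is where a claim for the whole range has to hold.

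It is also fair that the claim is true over most of the range (MAF 0.18 to 0.43), that the primary genotype analysis is additive and not dominant, and that the overview already concedes limited power in the 75 subjects. These limit the consequence. They do not make the sentence correct, since the plan itself chose the dominant model and the range 0.1 to 0.5. Finally, the plan claims no power for 0.5 SD; the figures for 0.5 SD bear only on the label.

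**Conclusion.** The statement for n = 75 is wrong as written. On the plan's dominant model, Hardy-Weinberg carrier shares and a single two-sided 0.05 test, power for 0.7 SD is 65% at MAF 0.1 and 74% at MAF 0.5, and the detectable difference over the range is 0.66 to 0.84 SD. The shortfall at MAF 0.1 holds under every variant tried; the shortfall at MAF 0.5 depends on two-sided testing.

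The n = 97 statement is slightly short at MAF 0.1 only (76%; 80% is reached from MAF 0.114), and the DPP statement is sound for one test. Since 0.7 is the rounded value of the n = 97 maximum, one figure may have been applied to both samples; that is inference.

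Calling 0.7 SD medium does not follow the section's own benchmarks. All these figures are for one test, while Aim 3 says "Approximately 1,500 htSNPs from 100 genes will be genotyped in" the three populations; any allowance for multiplicity would lower power further. This should be corrected, but no design decision rests on it.

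**What to change.** Replace the sentence for n = 75 and n = 97, and the DPP sentence with it, by something like:

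> For a single SNP test (dominant model, two-sided alpha 0.05, no allowance for the roughly 1,500 htSNPs), the difference detectable with 80% power over minor allele frequencies 0.1–0.5 is about 0.66–0.84 SD in the current study (n = 75), 0.57–0.73 SD in TRIPOD (n = 97) and 0.23–0.30 SD in the DPP.

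If a different alpha or sidedness was used, state it and recompute all the figures, including those for n = 38, on that basis. A narrower alternative is to keep 0.7 SD for n = 75 but limit it to MAF of about 0.18 to 0.43. Either way, drop the label medium for 0.7 SD and refer to the overview's caveat about the 75 subjects.

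The cost is wording only. Enrolment, endpoints and analyses stay as they are; the stated sensitivity of the 75-subject sample becomes less favourable.
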